5.6.2. Prohibited Medications and Non-Drug Therapies

Medications prohibited at specific time intervals prior to Visit 1 (and at any time during the study) are identified in the Exclusion Criteria (Section 4.3).

NOTE: All COPD medications (except for rescue albuterol/salbutamol, mucolytics and oxygen) are prohibited during the randomized period of the study except during the treatment of a moderate/severe COPD exacerbation or pneumonia. In the event of an exacerbation or pneumonia, sites should attempt to follow protocol treatment guidelines (Section 6.2.4); however, treatment with any medication that the health care provider deems necessary is allowed. Caution is advised in using a LABA or LAMA to treat a subject currently taking IP as these additional medications may increase the risk of overdose. If necessary the PI or other health care personnel may stop the subjects IP temporarily in order to treat the COPD exacerbation. Subjects who require more than two consecutive 14 day courses of treatment (i.e. antibiotics or corticosteroids) should be evaluated for their continuation on IP by the PI in consultation with the GSK medical monitor.

Eligible subjects will be allowed to continue their usual COPD medications during screening and the 2-week run-in period. On the morning of the Screening Visit subjects will refrain from taking their morning dose of their usual COPD medications until instructed to do so by clinic personnel. During the run-in period subjects will continue to use their usual COPD medications.

On the day before the Randomization visit, subjects will take their last dose of their usual COPD medications and will not use any other COPD medications (except for those allowed per protocol: rescue albuterol, oxygen, mucolytics and medications for the treatment of a COPD exacerbation or pneumonia) until the end of the study. Rescue albuterol/salbutamol can be used throughout the study as needed but must be withheld for at least 4 hours prior to conducting spirometry.

COPD Medications and non-drug therapies that are prohibited during the randomized portion of the study:

- Inhaled and systemic corticosteroids (Except for the short term treatment [≤ 14 days] of a COPD exacerbation or pneumonia.) *Note: Topical and ophthalmic*

corticosteroids, and localized corticosteroid injections (intra-articular and epidural) are allowed.

- Long and short acting muscarinic antagonists
- Long and short acting β 2 -agonists
- PDE4 inhibitors (roflumilast)

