6.2.5. Spirometry Testing

Spirometry measurements will be obtained using spirometry equipment that meets or exceeds the minimal performance recommendations of the ATS [[Miller, 2005](#)]. All subjects will have spirometry performed at Screening and each scheduled clinic visit during the treatment period. At the screening visit both pre- and post-albuterol/salbutamol spirometry measurements will be measured in order to assess eligibility and reversibility (see Section [6.2.5.1](#)). At Visits 2-7 (and discontinuation of IP

visit) both pre- and post-albuterol/salbutamol spirometry will be measured prior to the subject taking their morning dose of IP. For FEV₁ and FVC determinations, at least 3 acceptable spirometry efforts (with no more than 8) should be obtained. Acceptable spirometry efforts should have a satisfactory start of test and end of test (*e.g.* a plateau in the volume-time curve) and be free from artifacts due to cough, early termination, poor effort, obstructed mouthpiece, equipment malfunction, or other reasons [Miller, 2005].

The largest FEV₁ and FVC from the 3 acceptable efforts should be recorded, even if they do not come from the same effort.

Spirometry must be performed as follows:

- Started approximately between 6:00AM and 11:00AM.
- If applicable, after completing the health outcomes assessments (SGRQ-C, BDI/TDI, EQ5D, CAT, Activity limitation, HRU, COPD assessment).
- After withholding albuterol/salbutamol for ≥ 4 hours.
- At screening, before the morning dose of their usual COPD medications.
- At randomization and all treatment visits, before the morning dose of IP.
- Subjects should refrain from smoking for 1 hour prior to each pulmonary function test.
- Subjects should abstain from drinking beverages with high levels of caffeine such as tea and coffee for 2 hours prior to each pulmonary function test.

A full description of the timing and conduct of spirometry procedures is provided in the SPM.

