6.2.10. COPD Assessment Test (CAT)

The CAT will be completed by subjects at screening, randomization, Week 4, Week 28 and Week 52 (or IP Discontinuation Visit).

The COPD Assessment Test (Jones, 2009; Jones, 2012) is a validated, short and simple patient completed questionnaire which has been developed for use in routine clinical practice to measure the health status of patients with COPD. The CAT is an 8-item questionnaire suitable for completion by all patients diagnosed with COPD. When completing the questionnaire, subjects rate their experience on a 6-point scale, ranging from 0 (no impairment) to 5 (maximum impairment) with a scoring range of 0-40. Higher scores indicate greater disease impact.

6.2.11. Subject Global Rating of Activity Limitation and Subject Global Impression of Change in Activity Limitation

Subjects will complete the Global Rating of Activity Limitation at randomisation and all subsequent visits including the final visit (or IP Discontinuation Visit). This single global question will ask subjects to rate their activity limitation on a four-point scale (not limited, slightly limited, limited, very limited).

Subjects will complete a Global Impression of Change in Activity Limitation question at all visits subsequent to randomisation including the final visit (or IP Discontinuation Visit). Response options will be on a 7 point Likert scale ranging from much better to much worse.

(Note: The above assessments are in addition to the subject's daily diary recording of activity level that was affected by their respiratory symptoms.)

6.2.12. Subject Global Rating Severity of COPD and Subject Global Impression of Change in COPD

Subjects will complete the Global rating severity of COPD at randomization. This single global question will ask subjects to rate their severity of COPD on a four point scale (mild, moderate, severe, very severe).

Subjects will complete a Global Rating of Change in COPD (overall disease) question at all visits subsequent to randomisation including the final visit (or IP Discontinuation Visit). Response options will be on a 7 point Likert scale ranging from much better to much worse. Asking at each visit allows for early detection of response as well as continued response.

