**6.1.2. Disease Characteristics**

The screening lung function summary will include pre-bronchodilator and post-bronchodilator FEV1, FVC, FEV1/FVC ratio, FEV1 as a percentage of predicted normal, and FEV1 reversibility to salbutamol (expressed in milliliters [mL] and as a percentage). These assessments, with the exception of pre-bronchodilator FEV1/FVC ratio and pre-bronchodilator FEV1 as a percentage of predicted normal, will be collected in the eCRF and no recalculation of these values will be performed. Pre-bronchodilator FEV1/FVC ratio and pre-bronchodilator FEV1 as a percentage of predicted normal will be derived as

defined in Section 11.4.2 and Section 11.5.2.9. The reversibility to salbutamol status (Reversible or Non-reversible) will also be summarized as defined in Section 11.5.2.9.

COPD exacerbation history at screening (see Section 11.5.2.8) will be summarized with frequency distributions (0, 1, 2,  $\geq 3$  and  $\geq 2$ ) of the number of moderate exacerbations, the number of severe exacerbations, the number of moderate/severe exacerbations, the number of exacerbations treated with systemic/oral corticosteroids (with or without antibiotics), and the number of exacerbations treated with antibiotics (with or without systemic/oral corticosteroids). For each moderate/severe exacerbation the severity, duration, whether the exacerbation led to hospitalization, systemic/oral corticosteroids being taken and antibiotics being taken will be summarized. See Section 11.5.2.8 for the definition of exacerbation severity.

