**8.2. Trough FEV1 and SGRQ Total Score**

**8.2.1. Planned Primary Statistical Analyses for Trough FEV1 and SGRQ Total Score**

Secondary Statistical Analyses
Endpoint(s)

 
• Change from baseline in trough FEV1
 
• Change from baseline SGRQ total score
 

Model Specification

 
• Mixed Models Repeated Measures (MMRM) model.
 
• While missing data are not explicitly imputed in the primary MMRM analyses, there is an underlying assumption that the data are missing at random. All available scheduled post-baseline assessments will be utilized and via modeling of the within-subject correlation structure, the derived treatment differences will be adjusted to take into account missing data.
 
• The MMRM analysis for trough FEV1 will include on-treatment FEV1 measurements at Weeks 4, 16, 28, 40 and 52. The MMRM analysis for SGRQ total score will include on-treatment SGRQ total scores at Weeks 4, 28 and 52.
 
• Although the secondary endpoints are Change from baseline in trough FEV1 at Week 52 for
 

Secondary Statistical Analyses

FF/UMEC/VI vs. FF/VI and Change from baseline in SGRQ total Score at Week 52 for FF/UMEC/VI vs. FF/VI, results for all treatment comparisons at all time points where data are scheduled to be collected will be included in the analysis and presented in the displays.
 
 
• Terms in the model: 
 
• Response: trough FEV1 or SGRQ Total score at each visit.
 
• Categorical: treatment group, smoking status (screening), geographical region, visit
 
• Continuous: baseline FEV1 or baseline SGRQ Total score
 
• Interaction: baseline*visit, treatment group*visit
 
• Repeated: visit
 
 
 
• The model will be fit with an unstructured variance-covariance matrix.
 
• The Kenward and Roger method (KR) for approximating the denominator degrees of freedom and correcting for bias in the estimated variance-covariance of the fixed effects will be used. In the event the model fails to run using the KR method, then the residual method will be used instead.
 
• Baseline is defined in Section 11.4.2
 
• Two models will be fitted; one with a response variable of change from baseline and one with the response variable as the raw value.
 

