**11.4.2. Baseline Definitions & Derivations**

Parameter	Study Assessments Collected Prior to Dosing		Baseline Definition
	Screening	Day 1 Pre-Dose	
Efficacy and Health Outcomes			
Trough FEV1, Trough FVC	X	X	Day 1 pre-dose and pre-bronchodilator nominal time-point
Post-bronchodilator FEV1, Post-bronchodilator FVC	X	X	Day 1 pre-dose and post-bronchodilator nominal time-point
FEV1 reversibility (mL)	X	X	Day 1 FEV1 reversibility (mL)
SGRQ total and domain scores		X	Day 1
CAT score	X	X	Day 1
EQ-5D-5L		X	Day 1
BDI (TDI Baseline)		X	Day 1
Subject global ratings		X	Day 1
Mean number of occasions of rescue use, mean number of nighttime awakenings per night	X	X	Average of measurements from Day -13 to Day 1 inclusive (at least 7 days must be non-missing)
Percentage of rescue-free days, percentage of days symptoms stopped usual activities	X	X	Percentage is calculated as total number of rescue-free days (or total number of days symptoms stopped usual activities) divided by total number of days with non-missing value (from Day -13 to Day 1 inclusive (at least 7 days must be non-missing)) x100
Safety			
Blood pressure	X		Values from most recent assessment prior to first dose of study treatment which records both systolic and diastolic BP (generally Screening but could be a test repeat).
Pulse rate	X		Most recent individual value prior to first dose of study treatment

Parameter	Study Assessments Collected Prior to Dosing		Baseline Definition
	Screening	Day 1 Pre-Dose	
Laboratory tests: Excluding hematology	X		Most recent individual value prior to first dose of study treatment
Laboratory tests: Hematology (including blood eosinophils)	X	X	Most recent individual value prior to first dose of study treatment
ECG endpoints	X		Values from most recent ECG conducted prior to first dose of study treatment

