**NOTES :**

- Only records that have been assigned a treatment phase of 'pre-treatment' as defined in Section 11.3.3 will be considered as baseline assessments.
- Baseline Definitions will be used for derivations for endpoints / parameters and indicated on summaries and listings.
- Unless otherwise stated, if baseline data is missing no derivation will be performed and will be set to missing.

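### The FEV1, FVC, reversibility and CAT models adjust only for the Day 1 value, leaving unused a Screening reading of the same measure that would add a little precision

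*SAP*

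**What the plan says.** The baseline table in SAP 11.4.2 has one column for Screening and one for Day 1 pre-dose. Both are marked for trough and post-bronchodilator FEV1 and FVC, FEV1 reversibility and CAT. The baseline definition then uses Day 1 only: "Day 1 pre-dose and pre-bronchodilator nominal time-point" for trough values, "Day 1 pre-dose and post-bronchodilator nominal time-point" for post-bronchodilator values, and Day 1 for reversibility and CAT.

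The Screening measurements are scheduled for everyone. Protocol 6.2.5: "At the screening visit both pre- and post-albuterol/salbutamol spirometry measurements will be measured in order to assess eligibility and reversibility". Protocol 6.2.10: "The CAT will be completed by subjects at screening, randomization, Week 4, Week 28 and Week 52".

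In SAP 8.2.1 the only continuous covariate is "baseline FEV1 or baseline SGRQ Total score", with its visit interaction. SAP 9.1.2.6 applies that model to post-bronchodilator FEV1 and FVC, trough FVC, reversibility and CAT. SAP 9.1.2.5 applies it to the eosinophil-subgroup versions of trough FEV1 and CAT. The responder models in 9.1.2.7 also carry one baseline.

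No fallback is given. The notes to 11.4.2 say that, unless otherwise stated, "if baseline data is missing no derivation will be performed and will be set to missing". SAP 11.6 sets responder status to missing when baseline is missing.

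**The concern.** The two spirometry sessions are taken under similar conditions. Protocol 6.2.5 asks for a start between about 6 and 11 AM and at least 4 hours without albuterol at both. For Screening, Protocol 5.6.2 says "On the morning of the Screening Visit subjects will refrain from taking their morning dose of their usual COPD medications"; for randomization, the last dose of usual medication is taken the day before. Protocol 3.2 keeps that medication unchanged through the 2-week run-in.

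A single FEV1 or CAT reading carries day-to-day error. A second pre-treatment reading of the same quantity usually explains some further Week 52 variance, and here it already exists.

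The same table treats other measures differently. Diary baselines average the run-in, and hematology, collected at the same two visits, takes the most recent pre-dose value. FEV1, FVC and CAT get neither pooling nor fallback, and no reason is stated.

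What is at stake is confidence-interval width. Trough FEV1 against FF/VI is in Block 1 of the secondary hierarchy (SAP 11.9), where the thresholds are 0.04/0.025 if both co-primary comparisons succeed and 0.008/0.005 if only one does. Precision is scarcer in comparisons with the 2,000-subject UMEC/VI arm and within eosinophil subgroups. A subject without a usable Day 1 value also leaves both the change and the raw-value models, even with a valid Screening reading.

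**Working it through.** **Inputs.** The documents give no SD, correlation, power or sample size for FEV1, FVC or CAT, so there is no stated figure to reproduce, and every correlation below is an assumption. Let r be the correlation of a pre-treatment reading with Week 52, and b the correlation between the Screening and Day 1 readings. The formulas are for a complete-data ANCOVA at Week 52, which approximates the Week 52 contrast of a repeated-measures model with visit-specific baseline slopes.

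**Step 1: exchangeable readings.** Residual variance as a fraction of total:
- Day 1 only: 1 − r²
- both readings: 1 − 2r²/(1 + b)

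| Measure | r | b | Day 1 only | Both | Ratio | Reduction |
|---|---|---|---|---|---|---|
| FEV1 | 0.80 | 0.95 | 0.360 | 0.344 | 0.954 | 4.6% |
| FEV1 | 0.80 | 0.90 | 0.360 | 0.326 | 0.906 | 9.4% |
| FEV1 | 0.90 | 0.95 | 0.190 | 0.169 | 0.891 | 10.9% |
| FEV1 | 0.90 | 0.90 | 0.190 | 0.147 | 0.776 | 22.4% |
| CAT | 0.50 | 0.85 | 0.750 | 0.730 | 0.973 | 2.7% |
| CAT | 0.60 | 0.75 | 0.640 | 0.589 | 0.920 | 8.0% |

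Over the assumed ranges this is about 5-22% for FEV1 and 3-8% for CAT. For FEV1 the standard error falls by 2% (√0.954 = 0.977) to 12% (√0.776 = 0.881).

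**Step 2: Screening slightly less predictive.** With r1 for Day 1 and r2 for Screening:
- both as covariates: 1 − (r1² + r2² − 2·r1·r2·b)/(1 − b²)
- plain mean as covariate: 1 − (r1 + r2)²/(2(1 + b))

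Each is divided by 1 − r1²:

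| r1 | r2 | b | Both covariates | Plain mean |
|---|---|---|---|---|
| 0.80 | 0.77 | 0.90 | 0.963 | 0.976 |
| 0.80 | 0.75 | 0.90 | 0.987 | 1.022 |
| 0.85 | 0.82 | 0.92 | 0.966 | 0.986 |
| 0.70 | 0.65 | 0.85 | 0.979 | 0.995 |
| 0.60 | 0.55 | 0.80 | 0.979 | 0.988 |

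Two covariates still gain 1-4%. The plain mean ranges from a 2.4% gain to a 2.2% loss, so the two approaches are not interchangeable.

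**Step 3: bias and missing Day 1.** A simulation used 1,500 runs of 1,000 subjects per arm, a true difference of 0.1 SD, correlations of 0.80 (Day 1 with Week 52), 0.78 (Screening with Week 52) and 0.90 (between readings), and an assumed 2% of Day 1 values missing.
- Day 1 only: mean estimate 0.0997, SD 0.02736.
- Day 1 with Screening as fallback: 0.0997, SD 0.02702, variance ratio 0.975.
- Mean of the two with fallback: 0.0999, SD 0.02632, variance ratio 0.926.
- Among subjects selected on the Screening value: 0.0996 (Day 1) and 0.1000 (mean).

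All are unbiased, including after selection on Screening. The simulation did not run the two-covariate model; it shows the absence of bias and the small weight of missing Day 1 values.

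**Not calculated.** No figure is offered for FVC, reversibility or the responder models; the linear-model formulas do not carry over to odds ratios.

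**The case against.** The strongest reply is that nothing here is wrong. Day 1 pre-dose is the last value before treatment, it is pre-specified and already adjusted for by visit, and Protocol 8.3.5.1 also names a single baseline covariate. About 8,000 subjects (4,000 + 4,000) are planned for the FF/VI comparison. That stands: this is an efficiency refinement.

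The reply also questions whether Screening is an interchangeable repeat, and this largely stands too. Screening is the selection visit, with CAT of at least 10 and post-bronchodilator limits required there (Protocol 4.2). An exacerbation may have resolved only 14 days earlier (exclusion 7). A spacer is specified for Visit 1, whereas footnote d to Protocol Table 4 mentions only four puffs at later visits. The exchangeable figures are therefore optimistic, which is why the 1-4% case is shown and the plain mean is not recommended. Lower predictiveness shrinks the gain from a second covariate; it does not bias the randomized contrast.

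A second covariate alone would not rescue a subject with no Day 1 value, and would drop one with no Screening value. That is correct, and the fix needs an explicit fill rule.

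A reader might infer that every interval from these models is too wide, or that many subjects are lost. The documents support neither. SGRQ and TDI have no Screening value in 11.4.2. Day 1 spirometry is scheduled for all subjects, and no count of missing values is given.

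**Conclusion.** The point holds as a minor matter of efficiency. For trough and post-bronchodilator FEV1 and FVC, reversibility and CAT, a pre-treatment reading already collected is left out of the models, at some cost in precision. The gain rests wholly on assumed correlations: about 5-22% lower residual variance for FEV1 (b 0.90-0.95, r 0.80-0.90) and 3-8% for CAT (b 0.75-0.85, r 0.50-0.60) if the readings are exchangeable, and about 1-4% if Screening correlates 0.03-0.05 less with Week 52.

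It would be tempting to read this as bias, or as a threat to the trough FEV1 result. Neither follows: adjusting for Day 1 alone leaves the randomized difference unbiased, and the conclusion against FF/VI is unlikely to change. The co-primary analysis is unaffected, since it does not use this baseline and adjusts for Screening percent predicted FEV1. Missing Day 1 values are probably few.

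**What to change.** In SAP 8.2.1 (trough FEV1 only), 9.1.2.5, 9.1.2.6 and 9.1.2.7:

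- Keep Day 1 and Day 1 by visit. Add the Screening value of the same measure and its visit interaction: pre-bronchodilator for trough models, post-bronchodilator for post-bronchodilator models, Screening reversibility for reversibility, Screening CAT for CAT. Do not replace the two values by their mean.
- If one of the two values is missing, fill that covariate from the other.
- Keep Day 1 as the reference for reported change and responder status. A subject without Day 1 is then rescued only in the raw-value model.
- Limit the wording to these measures, because SGRQ, TDI and the diary endpoints share the 8.2.1 method.
- List the addition in SAP 2.1 as a change from Protocol 8.3.5.1, and make it before unblinding.

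No new data are needed. The extra parameters are one slope per visit: five for trough FEV1 (Weeks 4, 16, 28, 40, 52) and three for CAT (Weeks 4, 28, 52). Because the raw-value model may then hold a few more subjects than the change model, the two treatment differences could diverge slightly, so the SAP should say which one supplies the Block 1 p-value. If the sponsor prefers Day 1 alone, one sentence giving the reason would suffice.

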**NOTES :**

- Only records that have been assigned a treatment phase of 'pre-treatment' as defined in Section 11.3.3 will be considered as baseline assessments.
- Baseline Definitions will be used for derivations for endpoints / parameters and indicated on summaries and listings.
- Unless otherwise stated, if baseline data is missing no derivation will be performed and will be set to missing.

**11.4.3. Reporting Process & Standards**

Reporting Process	
Software	

 
• The currently supported versions of SAS and TCSG software will be used.
 
	
Reporting Area	
HARP Server	: UK1SALX00175
HARP Area	: /arenv/arprod/gsk2834425/ctt116855/final_01
QC Spreadsheet	: /arenv/arwork/gsk2834425/ctt116855/final_01/documents
Analysis Datasets	

 
• Analysis datasets will be created according to CDISC standards (SDTM Implementation Guide Version 3.1.3 & ADaM Implementation Guide Version 1.0).
 
• For creation of ADaM datasets (ADCM/ADAE), the same version of dictionary datasets will be implemented for conversion from SI to SDTM.
 
	
Generation of RTF Files	

 
• Rich Text Format (RTF) files will be generated for the final reporting effort for use in writing the CSR.
 
	

Reporting Standards	
General	

 
• The current GSK Integrated Data Standards Library (IDSL) will be applied for reporting, unless otherwise stated:
 
	

Reporting Standards	

 
○ 4.03 to 4.23: General Principles
 
○ 5.01 to 5.08: Principles Related to Data Listings
 
○ 6.01 to 6.11: Principles Related to Summary Tables
 
○ 7.01 to 7.13: Principles Related to Graphics
 
	
Formats	

 
● All data (including data collected post-study treatment discontinuation) will be reported according to the treatment to which the subject was randomized unless otherwise stated. However, there may be additional adhoc displays for individual subjects using the actual treatment received.
 
● GSK IDSL Statistical Principles (5.03 & 6.06.3) for decimal places will be adopted for reporting of eCRF data based on the raw data collected.
 
● The reported precision from non eCRF sources will follow the IDSL statistical principles but may be adjusted to a clinically interpretable number of decimal places.
 
● Summaries of continuous data will include number of subjects, mean, standard deviation, median, first quartile, third quartile, minimum and maximum,
 
● Percentages between 1% and 99%, inclusive, will be rounded to integers. Percentages greater than 0%, but less than 1%, will be reported as <1%, and percentages greater than 99%, but less than 100%, will be reported as >99%.
 
● Numeric data will be reported at the precision collected in the eCRF.
 
	
Planned and Actual Time	

 
● Reporting for tables, figures and statistical analyses: 
 
○ Planned time relative to dosing will be used in figures, summaries, statistical analyses and calculation of any derived parameters, unless otherwise stated. Actual time will be used for calculation of times to events and Kaplan-Meier plots.
 
 
 
● Reporting for listings: 
 
○ Planned and actual time relative to study treatment dosing will be shown in listings (refer to IDSL Statistical Principle 5.05.1).
 
 
 
	
Unscheduled Visits	

 
● Unscheduled visits will not be included in summary tables except as part of a maximum/minimum/worst case post-baseline assessment or if they are assigned as the baseline assessment as detailed in Section 11.4.2.
 
● All unscheduled visits/unplanned readings will be included in listings.
 
	
Cardiovascular Event Reports	

 
● Laboratory results, ECG results/findings and vital signs measurements collected as part of cardiovascular event reports will not be included in any tables, listings or any minimum/maximum post-baseline assessments.
 
	
Descriptive Summary Statistics	
Continuous Data	Refer to IDSL Statistical Principle 6.06.1
Categorical Data	N, n, frequency, %
p-value	

 
● Both adjusted and unadjusted p-values will be displayed on the primary analyses outputs for
 
	

Reporting Standards

the endpoints within the hierarchy (detailed in Section 11.9) and will be labeled 'Adjusted p-value' and 'Unadjusted p-value'
 

• All other p-values will be unadjusted and labeled purely as 'p-value'.

Time to event results

• For all time to event analyses, the first quartile and median time to event will be presented. If less than 25% of subjects experienced the event within a treatment group then the first quartile will be displayed as NA (not applicable) for that treatment. If less than 50% of subjects experienced the event within a treatment group then the median will be displayed as NA (not applicable) for that treatment.

Graphical Displays

• Refer to IDSL Statistical Principals 7.01 to 7.13.

